#### **6.5.2.1 Laboratory Test Abnormalities**

Refer to the BHV3000 Core SAP for toxicity grade categories and additional details.

---

## **Worst Laboratory Test Abnormalities**

The number and percentage of subjects with the worst (highest) laboratory test abnormality in a safety analysis period will be presented by treatment group (and overall if applicable) in toxicity grade categories separately for each graded laboratory test.

Worst laboratory test abnormalities will be summarized for the following safety analysis periods and populations: on-DBT for treated subjects; on-DB or OL rimegepant for DB or OL rimegepant treated subjects; post-DBT pre-OL rimegepant for interim subjects; on-OL rimegepant for OL rimegepant treated subjects by overall for the 90-Day Safety Update only; on-treatment for treated subjects by overall for the 90-Day Safety Update only; follow-up for follow-up subjects.

Worst laboratory test abnormalities will also be summarized for the following safety analysis periods and populations by subgroup level and overall for all safety subgroups of interest described in Sections 6.1.3.2, 6.1.3.3 and 6.1.3.4: on-DBT for treated subjects for each treatment group; on-DB or OL rimegepant for DB or OL rimegepant treated subjects; on-OL rimegepant for OL rimegepant treated subjects.

## **Laboratory Test Toxicity Grade Shifts From Baseline to Worst Abnormality**

Laboratory test toxicity grade shifts from baseline to the worst (highest) toxicity grade in the safety analysis period will be summarized by treatment group (and overall if applicable) as the number and percentage of subjects in each toxicity grade category.

Shifts will be summarized for the following safety analysis periods and populations: (1) on-DBT for treated subjects, and (2) on-DB or OL rimegepant for DB or OL rimegepant treated subjects, using DB or OL rimegepant baseline instead of baseline.

Shifts will also be summarized for the following safety analysis periods and populations by subgroup level and overall for all safety subgroups of interest described in Sections 6.1.3.3 and 6.1.3.4: on-DB or OL rimegepant for DB or OL rimegepant treated subjects, using DB or OL rimegepant baseline instead of baseline; on-OL rimegepant for OL rimegepant treated subjects, using OL rimegepant baseline instead of baseline.

## **Laboratory Test Low/Normal/High Shifts From Baseline to any Abnormal Value**

Laboratory test low/normal/high shifts from baseline to any abnormal value in the safety analysis period will be summarized by treatment group (and overall if applicable) as the number and percentage of subjects in each category for laboratory tests with normal ranges.

Shifts will be summarized for the following safety analysis periods and populations: (1) on-DBT for treated subjects, and (2) on-DB or OL rimegepant for DB or OL rimegepant treated subjects, using DB or OL rimegepant baseline instead of baseline.

Shifts will also be summarized for the following safety analysis periods and populations by subgroup level and overall for all safety subgroups of interest described in Sections 6.1.3.3 and

---

6.1.3.4: on-DB or OL rimegepant for DB or OL rimegepant treated subjects, using DB or OL rimegepant baseline instead of baseline; on-OL rimegepant for OL rimegepant treated subjects, using OL rimegepant baseline instead of baseline.

#### 6.5.2.2 LFT Elevations

Subjects must have non-missing LFT data (i.e., ALT, AST, TBL, or ALP) in the safety analysis period to be included.

Refer to the BHV3000 Core SAP for additional details.

#### LFT Elevations

The number and percentage of subjects with pre-specified cumulative, mutually exclusive, and composite LFT elevations will be summarized by treatment group (and overall if applicable) separately for the following safety analysis periods and populations:

- Pre-treatment for treated subjects
- Pre-rimegepant treatment for DB or OL rimegepant treated subjects
- On-DBT for treated subjects (excluding overall)
- On-DB or OL rimegepant for DB or OL rimegepant treated subjects
- On-DB or OL rimegepant for DB or OL rimegepant treated subjects by subgroup level and overall for all safety subgroups of interest described in Sections 6.1.3.3
- Post-DBT pre-OL rimegepant for interim subjects
- On-OL rimegepant for OL rimegepant treated subjects by overall for the 90-Day Safety Update only
- On-OL rimegepant for OL rimegepant treated subjects by subgroup level and overall for all safety subgroups of interest described in Sections 6.1.3.4
- On-treatment for treated subjects by overall for the 90-Day Safety Update only
- Follow-up for follow-up subjects.

The following LFT elevations will be summarized for: (1) on-DBT for treated subjects, and (2) on-DB or OL rimegepant for DB or OL rimegepant treated subjects:

- Exposure-adjusted cumulative LFT elevations with the number and percentage of subjects with LFT elevations, along with patient-years and exposure-adjusted rates based on exposure up to time of first LFT elevation (see Section 7.6.1).
- Time to first LFT elevation with number and percentage of subjects with LFT elevations by time categories (weeks):  $\leq 2$ ,  $> 2$  to  $\leq 4$ ,  $> 4$  to  $\leq 8$ , and additional 4-week intervals. LFT elevations are ALT  $> 3 \times$  ULN, AST  $> 3 \times$  ULN, and ALT or AST  $> 3 \times$  ULN. Subjects must have an LFT elevation in the safety analysis period to be included.

#### LFT ULN Shifts From Baseline to Worst Elevation

---

LFT ULN shifts from baseline to the worst (highest) elevation in the safety analysis period will be summarized by treatment group and overall as the number and percentage of subjects in pre-specified LFT elevation categories.

Shifts will be summarized for the following safety analysis periods and populations: (1) on-DBT for treated subjects; and (2) on-DB or OL rimegepant for DB or OL rimegepant treated subjects, using rimegepant baseline instead of baseline.

Shifts will also be summarized for the following safety analysis periods and populations by subgroup level and overall for all safety subgroups of interest described in Sections 6.1.3.3 and 6.1.3.4: on-DB or OL rimegepant for DB or OL rimegepant treated subjects, using DB or OL rimegepant baseline instead of baseline; on-OL rimegepant for OL rimegepant treated subjects, using OL rimegepant baseline instead of baseline.

### **eDISH Scatter Plots**

An evaluation of drug-induced serious hepatotoxicity (eDISH) scatter plot will display the maximum TBL ratio of value to ULN (y-axis) versus the maximum ALT ratio of value to ULN (x-axis), where both maxima will be in the same safety analysis period but not necessarily concurrent. eDISH scatter plots will be produced by treatment group for the following safety analysis periods and populations: (1) on-DBT for treated subjects; (2) on-DB or OL rimegepant for DB or OL rimegepant treated subjects.

eDISH scatter plots will also be produced for the following safety analysis periods and populations by mutually-exclusive subgroup level for all safety subgroups of interest described in Sections 6.1.3.3 and 6.1.3.4: on-DB or OL rimegepant for DB or OL rimegepant treated subjects; on-OL rimegepant for OL rimegepant treated subjects.

### **By-Subject Longitudinal LFT Plots**

By-subject longitudinal plots will display ratios of values to ULN for AST, ALT, ALP, and TBL (y-axis) versus study week of the laboratory test result (x-axis) for treated subjects with any of the following LFT elevations in a safety analysis period (pre-treatment, on-treatment, follow-up): ALT > 3 x ULN, AST > 3 x ULN, TBL > 2 x ULN, or ALP > 2 x ULN. Study weeks are defined as study day/7, where study day is derived from the laboratory test collection date (see Section 7.5). Each figure will also display DBT and OL rimegepant dosing days using symbols along the x-axis (see Section 7.6.2), start of DBT, start of OL rimegepant, and start of the follow-up safety analysis period using vertical lines.

#### **6.5.2.3      *Laboratory Test Changes From Baseline Over Time***

Values and changes from baseline in all hematology and serum chemistry laboratory tests will be summarized using descriptive statistics by treatment group and overall for treated subjects at the following time points: baseline; each scheduled visit through Week 12 and EOT of the on-DBT safety analysis period; each scheduled visit from Week 12 through EOT of the on-OL rimegepant safety analysis period; each scheduled visit and EOFU of the follow-up safety analysis period.

---

Values and changes from rimegepant baseline in all hematology and serum chemistry laboratory tests will be summarized analogously for DB or OL rimegepant treated subjects at the following time points: rimegepant baseline; each scheduled visit and EOT of the on-DB or OL rimegepant safety analysis period; each scheduled visit and EOFU of the follow-up safety analysis period. Note that scheduled visits vary according to laboratory test (see Section 6.5.2).

### **6.5.3 Vital Signs and Physical Measurements**

Vital signs and physical measurements will be measured at early termination and the following visits: screening; baseline; Weeks 4, 8, and 12 of the DBT phase; Week 16 and every 4 weeks through Week 64 of the OLE phase; and follow-up Week 2.

Vital signs will include systolic blood pressure, diastolic blood pressure, heart rate, temperature, and respiratory rate. In summaries, only vital signs measured in the sitting position will be included. Physical measurements will include weight and BMI.

A by-subject listing of vital signs and physical measurements will be provided for enrolled subjects.

#### **6.5.3.1 Vital Sign and Physical Measurement Changes From Baseline Over Time**

Values and changes from baseline in vital sign and physical measurement parameters will be summarized as continuous parameters by treatment group and overall for treated subjects at the following time points: baseline; Weeks 4, 8, 12, and EOT of the on-DBT safety analysis period; Week 16, every 4 weeks through Week 64, and EOT of the on-OL rimegepant safety analysis period; follow-up Week 2 and EOFU of the follow-up safety analysis period.

Values and changes from rimegepant baseline in vital sign and physical measurement parameters will be summarized analogously for DB or OL rimegepant treated subjects at the following time points: rimegepant baseline; Week 4, every 4 weeks through Week 64, and EOT of the on-DB or OL rimegepant safety analysis period; follow-up Week 2 and EOFU of the follow-up safety analysis period.

#### **6.5.3.2 Vital Sign and Physical Measurement Abnormalities**

Vital sign and physical measurement abnormalities in safety analysis periods will be summarized by treatment group and overall as the number and percentage of subjects in prespecified categories defined in the BHV3000 Core SAP.

Abnormalities will be summarized for the following safety analysis periods and populations: (1) on-DBT for treated subjects; (2) on-DB or OL rimegepant for DB or OL rimegepant treated subjects, using DB or OL rimegepant baseline instead of baseline for weight change; and (3) follow-up for follow-up subjects.

Abnormalities will also be summarized for the following safety analysis periods and populations by subgroup level and overall for all safety subgroups of interest described in Sections 6.1.3.3 and 6.1.3.4: on-DB or OL rimegepant for DB or OL rimegepant treated subjects, using DB or OL

rimegepant baseline instead of baseline for weight change; on-OL rimegepant for OL rimegepant treated subjects, using OL rimegepant baseline instead of baseline for weight change.

#### **6.5.4 Electrocardiograms**

ECGs will be measured at early termination and the following visits: screening; baseline; Week 4 of the DBT phase; and Weeks 16, 24, 48, and 64 of the OLE phase; and follow-up Week 2. ECG parameters will include RR, QRS, PR, QT, QTcF, QTcB, and ventricular heart rate.

A by-subject listing of ECG results will be provided for enrolled subjects.

##### **6.5.4.1 ECG Changes From Baseline Over Time**

Values and changes from baseline in ECG parameters will be summarized as continuous parameters by treatment group and overall for treated subjects at the following time points: baseline; Week 4 and EOT of the on-DBT safety analysis period; Weeks 16, 24, 48, 64 and EOT of the on-OL rimegepant safety analysis period; follow-up Week 2 and EOFU of the follow-up safety analysis period.

Values and changes from rimegepant baseline in ECG parameters will be summarized analogously for DB or OL rimegepant treated subjects at the following time points: rimegepant baseline; Weeks 4, 16, 24, 48, 64, and EOT of the on-DB or OL rimegepant safety analysis period; follow-up Week 2 and EOFU of the follow-up safety analysis period.

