### **6.5.2 Laboratory Tests**

Clinical safety laboratory testing will be performed at early termination and the following visits: screening; baseline; Weeks 4, 8, and 12 of the DBT phase; and Weeks 16, 24, 48 and 64 of the OLE phase. Urinalysis will be collected at early termination and the following visits: baseline; and Weeks 24 and 64 of the OLE phase. Lipids (i.e., cholesterol, high-density lipoprotein (HDL) cholesterol, low-density lipoprotein (LDL) cholesterol, and triglycerides) will be collected at early termination and the following visits: baseline; and Weeks 24 and 64 of the OLE phase. LFTs (ALT, AST, alkaline phosphatase [ALP], TBL, and direct bilirubin) will be collected routinely at early termination and the following visits: screening; pre-randomization lab visit; baseline; Weeks 2, 4, 8, and 12 of the DBT phase; Weeks 14, 16, and every 4 weeks through Week 64 of the OLE phase; and follow-up Weeks 2 and 8.

Clinically significant laboratory abnormalities will be identified as grade 3 to 4 laboratory test results. Refer to the BHV3000 Core SAP for laboratory tests of clinical interest and toxicity grading. Laboratory test groups of clinical interest will include hematology, serum chemistry, and urinalysis.

LDL cholesterol and triglycerides will be analyzed as separate laboratory test parameters according to fasting status: fasting (i.e., fasting status of yes), not fasting (i.e., fasting status not equal to yes, including no, unknown, not reported, missing, etc.), and overall.

Estimated glomerular filtration rate (eGFR) will be derived using the modification of diet in renal disease (MDRD) formula; refer to the BHV3000 Core SAP for additional details.

Tables, listings, and figures (TLFs) will be provided to show data in both Systeme Internationale (SI) and United States (US) unit systems, if applicable.

Tables will present results by treatment group (and overall if applicable), and laboratory tests alphabetically within laboratory test group, as applicable.

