    - Study drug end date/time: Latest study drug date/time.
    - Study drug last date/time:
      - Interim database lock: Study drug end date/time date derived only for subjects who have either (1) non-missing DB completion status on the DB Subject Status CRF, not continuing to OL on the DB Subject Status CRF, and missing OL rimegepant start date/time, or (2) non-missing OL completion status on the OL Subject Status CRF.
      - Final database lock: Study drug end date/time.
-

- DBT start date/time: Earliest DBT study drug date/time. This should be equal to study drug start date/time.
  - DBT end date/time: Latest DBT study drug date/time.
  - DBT last date/time:
    - Interim database lock or snapshot prior to Week 12 Interim Analysis database lock: DBT end date/time date derived only for subjects with non-missing DB study completion status on DB Subject Status CRF.
    - Database locks at or after Week 12 Interim Analysis database lock: DBT end date/time.
  - OL rimegepant start date/time: Earliest OL rimegepant study drug date/time.
  - OL rimegepant end date/time: Latest OL rimegepant study drug date/time.
  - OL rimegepant last date/time:
    - Database lock or snapshot prior to final database lock: OL rimegepant end date/time date derived only for subjects with non-missing OL study completion status on OL Subject Status CRF or non-missing follow-up study completion status on the Follow-up Subject Status CRF.
    - Final database lock: OL rimegepant end date/time.
  - DB or OL rimegepant start date/time: Study drug start date/time for subjects whose as-treated treatment group is rimegepant; OL rimegepant start date/time for subjects whose as-treated treatment group is placebo.
  - DB or OL rimegepant end date/time: Study drug end date/time for subjects whose as-treated treatment group is rimegepant; OL rimegepant end date/time for subjects whose as-treated treatment group is placebo.
  - DB or OL rimegepant last dose date/time: Study drug last date/time for subjects whose as-treated treatment group is rimegepant; OL rimegepant last date/time for subjects whose as-treated treatment group is placebo.
  - Other eDiary dates:
    - Headache start date/time: Complete reference time point date/time from the headache start question from the evening report headache log.
    - Headache end date/time: Complete reference time point date/time from the headache end question from the evening report headache log or follow-up headache log.

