## 7.5 Analysis Visit Windows

Refer to BHV3000-305 Protocol Section 4.3 (Tables 1 and 2) for the schedule of assessments.

Randomization days are calculated from randomization as follows:

- Measurement date – IWRS randomization date + 1, if measurement date  $\geq$  IWRS randomization date
- Measurement date – IWRS randomization date, if measurement date  $<$  IWRS randomization date.

Study days are calculated from study drug start as follows:

- Measurement date – study drug start date + 1, if measurement date  $\geq$  study drug start date
- Measurement date – study drug start date, if measurement date  $<$  study drug start date.

Rimegepant study days are calculated from DB or OL rimegepant start as follows:

- Measurement date – DB or OL rimegepant start date + 1, if measurement date  $\geq$  DB or OL rimegepant start date
- Measurement date – DB or OL rimegepant start date, if measurement date  $<$  DB or OL rimegepant start date.

Follow-up days are calculated from the study drug last as follows:

- Measurement date – study drug last date + 1, if measurement date/time  $\geq$  study drug last date
- Measurement date – study drug last date, if measurement date  $<$  study drug last date.

Analysis visit windows presented in Table 4 below are based on study days (see Section 7.4).

---

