# Denotes an extended visit in the analysis period and is displayed only in listings

Study days are used to define analysis visit windows in all analysis periods except on-rimegepant and follow-up safety. Rimegepant study days are used to define analysis visit windows in the on-DB or OL rimegepant safety analysis period. Follow-up days are used to define analysis visit windows in the follow-up safety analysis period.

Analysis visit windows in the on-DB or OL rimegepant safety analysis period are defined analogously to those in the on-treatment safety analysis period.

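### The ECG table of change from rimegepant baseline windows crossover subjects on a restarted clock but lists the double-blind arm's visit weeks, so its Week 16-64 rows are essentially one-arm

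*SAP*

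**What the plan says.** The table at issue is the second one in SAP 6.5.4.1, change from rimegepant baseline for DB or OL rimegepant treated subjects. It is shown by treatment group and overall, and its on-treatment time points are "rimegepant baseline; Weeks 4, 16, 24, 48, 64, and EOT of the on-DB or OL rimegepant safety analysis period".

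The clock for that period is set in SAP 7.5: "Rimegepant study days are used to define analysis visit windows in the on-DB or OL rimegepant safety analysis period". A rimegepant study day on or after the start is "Measurement date – DB or OL rimegepant start date + 1". SAP 7.3 defines the start as the "OL rimegepant start date/time for subjects whose as-treated treatment group is placebo". The windows themselves carry over from SAP Table 4: "Analysis visit windows in the on-DB or OL rimegepant safety analysis period are defined analogously to those in the on-treatment safety analysis period".

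ECG collection does not move with that clock. SAP 6.5.4 schedules ECGs at "Week 4 of the DBT phase; and Weeks 16, 24, 48, and 64 of the OLE phase", and Protocol Table 2 applies the same open-label schedule to everyone in the extension.

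For laboratory tests, SAP 6.5.2.3 prints no week list for the rimegepant period. It says "each scheduled visit and EOT of the on-DB or OL rimegepant safety analysis period" and notes that scheduled visits differ by test. Clinical safety laboratory tests are scheduled at "Weeks 4, 8, and 12 of the DBT phase; and Weeks 16, 24, 48 and 64 of the OLE phase" (SAP 6.5.2). LFTs run every 4 weeks from Week 16 through Week 64.

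**The concern.** The displayed weeks fit a subject whose rimegepant clock equals the study clock, that is, one who received rimegepant in the double-blind phase. They do not fit a subject who began rimegepant about 12 weeks later. The parallel vital-signs table in SAP 6.5.3.1 uses Week 4 and then every 4 weeks through Week 64, which accommodates both groups. Nothing in the SAP says that crossover ECGs are meant to be left out of the visit rows, so the ECG list looks like an oversight.

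The table describes all subjects exposed to rimegepant, relative to their own rimegepant baseline. SAP 6.5 names the on-rimegepant period as one of primary interest for unblinded reports, and SAP 4 directs the Addendum Report to safety in the DB or OL rimegepant phase. A reader would take the overall column at Weeks 16 to 64 as pooled experience when it is close to a single arm.

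**Working it through.** **Inputs.** ECG visit days come from Protocol Tables 1 and 2: Week 4 = Day 28, Week 16 = Day 112, Week 24 = Day 168, Week 48 = 48 × 7 = Day 336, Week 64 = Day 448, with ±3 days for the extension visits. Windows come from SAP Table 4: Week 2 = 1-21, Week 4 = 22-42, Week 8 = 43-70, Week 12 = 71-91, Week 16 = 106-126, Week 24 = 155-182, Week 32 = 211-238, Week 36 = 239-266, Week 48 = 323-350, Week 52 = 351-378, Week 64 = 435-462.

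The open-label start day is an assumption. The Week 12 visit is Day 84 and dosing waits for laboratory results, so I take study days 85-98.

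**Step 1, the plan's own list.** For subjects on double-blind rimegepant, rimegepant day = study day. Days 28, 112, 168, 336 and 448 fall in the Week 4, 16, 24, 48 and 64 windows. This reproduces the listed weeks exactly.

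**Step 2, crossover subjects, visits on target.** Rimegepant day = study visit day − open-label start day + 1. Each cell gives rimegepant day → window.

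| Open-label start (study day) | ECG at day 112 | ECG at day 168 | ECG at day 336 | ECG at day 448 |
|---|---|---|---|---|
| 85 | 28 → Week 4 | 84 → Week 12 | 252 → Week 36 | 364 → Week 52 |
| 91 | 22 → Week 4 | 78 → Week 12 | 246 → Week 36 | 358 → Week 52 |
| 92 | 21 → Week 2 | 77 → Week 12 | 245 → Week 36 | 357 → Week 52 |
| 98 | 15 → Week 2 | 71 → Week 12 | 239 → Week 36 | 351 → Week 52 |
| 99 | 14 → Week 2 | 70 → Week 8 | 238 → Week 32 | 350 → Week 48 |

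Of these windows, only Weeks 4 and 48 have a row. For starts on days 85-98 with on-target visits, the second to fourth ECGs never reach a numbered row. The first reaches one only for starts through day 91.

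**Step 3, visits within ±3 days.** There are 14 start days × 7 visit offsets = 98 combinations for each ECG. For the second, third and fourth ECGs, 92 of 98 give Weeks 12, 36 and 52. The other 6 give Weeks 8, 32 and 48, of which only Week 48 is displayed. The first ECG falls in Week 4 in 49 combinations and in Week 2 in 49.

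**Step 4, how many ECGs have no row.** EOT is the last non-missing value in the period (SAP 6.5), so a completer's study Week 64 ECG is shown there. That leaves mainly the study Week 24 and 48 ECGs, two per subject. About 675 subjects are expected in the extension. With near-equal continuation by arm, half is about 338, and I use 300-375. Then 2 × 300 = 600 and 2 × 375 = 750 ECGs before dropout. For starts from day 92, the study Week 16 ECG is additional.

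**Step 5, laboratory tests.** With a start on day 85, the clinical laboratory draws at study Weeks 16, 24, 48 and 64 fall at rimegepant Weeks 4, 12, 36 and 52. Weeks 4 and 12 are scheduled for these tests, but 36 and 52 are not. Crossover LFT visits (checked for starts on days 85, 88 and 91) all fall in a scheduled LFT week.

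**The case against.** The strongest reply is that this is a gap in the row list of one descriptive table and that nothing is hidden. Much of that stands.

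- The first table in SAP 6.5.4.1, on the study-day clock, shows the same crossover ECGs at Weeks 16, 24, 48, 64 and EOT by treatment group. Only the baseline differs: pre-double-blind instead of rimegepant baseline. Double-blind ECGs are scheduled only at baseline and Week 4, so a placebo subject's rimegepant baseline is normally the Week 4 ECG. Both baselines are off rimegepant and about four weeks apart.
- The interpretation shifts (6.5.4.2) and abnormality tables (6.5.4.3) cover the whole on-rimegepant period and do not depend on visit rows. All ECGs are listed by subject.
- The table is split by treatment group, so row counts would reveal who contributes.
- The Mock TLF documents that SAP 7.1.1 points to may print other rows. They are not available here.

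A reader might infer that crossover ECGs are lost, or that the placebo-arm column is empty. The documents do not support either. Crossover subjects can appear at Week 4, EOT, follow-up Week 2 and end of follow-up. Late starts, off-target visits and early-termination ECGs can also put a few values in the other rows. Nor does the point reach liver monitoring, because the LFT schedule is dense enough.

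What survives is that the SAP text pairs one group's visit list with a clock that differs by group. The companion table does not give change from rimegepant baseline by visit for everyone exposed.

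**Conclusion.** The mismatch is real and limited. Followed as written, SAP 6.5.4.1 produces numbered Week 16-64 ECG rows that hold essentially only subjects given double-blind rimegepant, in a table labelled for all DB or OL rimegepant treated subjects. Mainly the study Week 24 and 48 ECGs of crossover subjects have no row in this table, with the size worked out above.

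This rests on open-label starts on study days 85-98, visits near target, and near-equal continuation by arm. From day 99 the on-target study Week 64 ECG falls in the displayed Week 48 row, while the study Week 24 and 48 ECGs fall at Weeks 8 and 32, still without a row.

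The laboratory part is weaker. It is inferred from the reference to scheduled visits, and it concerns haematology and non-LFT chemistry at study Weeks 48 and 64 only. It would go too far to say that a late ECG or laboratory trend is concealed. This is a display rule to correct, with no effect on efficacy or on the worst-value safety tables.

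**What to change.** In SAP 6.5.4.1, display the on-DB or OL rimegepant ECG visits at Week 2, every 4 weeks through Week 64, and EOT, similar to vital signs in 6.5.3.1. At the least, add Weeks 2, 12, 36 and 52 to the present list. The 4-weekly version also catches the few values at Weeks 8 and 32. Add a footnote saying which arm contributes to which row, noting that a crossover subject's first open-label ECG may fall in Week 2 or Week 4.

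In SAP 6.5.2.3, state that scheduled visits in the rimegepant period include rimegepant Weeks 36 and 52 for haematology and non-LFT chemistry. For open-label starts from day 92, the study Week 16 draw falls in Week 2, so the text should say where it is shown. LFT rows need no change.

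The cost is some extra rows and a footnote, with no new data. The drawback is that many added rows will be largely single-arm, so the overall column still will not pool both groups at most weeks. The footnote has to make that plain.
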